# APPENDIX C: DIAGNOSTIC SCORING TABLE FOR FAMILIAL HYPERCHOLESTEROLEMIA (CONSTRUCTED BY THE DUTCH LIPID CLINIC NETWORK)

Criteria	Score			
Family history				
a) First-degree relative known with premature (men <55 years, women <60 years) coronary a	and			
vascular disease; OR				
b) First-degree relative known with LDL-C >95 th percentile; AND/OR	1			
a) First-degree relative with tendon xanthomata and/or arcus cornealis; OR				
b) Children <18 years with LDL-C >95 th percentile.	2			
Clinical history				
a) Patient has premature (men <55 years, women <60 years) coronary artery disease	2			
b) Patient has premature (men <55 years, women <60 years) cerebral or peripheral vascular				
disease	1			
Physical examination				
a) Tendon xanthomata	6			
b) Arcus cornealis below the age of 45 years	4			
Laboratory analysis 				
a) LDL-C >330 mg/dL (>8.5 mmol/L)				
b) LDL-C 250-329 mg/dL (6.5-8.5 mmol/L)				
c) LDL-C 190-249 mg/dL (4.9-6.4 mmol/L)				
d) LDL-C 155-189 mg/dL (4.0-4.9 mmol/L)				
DNA analysis				
a) Presence of functional LDL-R mutation (in the LDL-R, ApoB, or PCSK9 gene)	8			
Diagnosis of familial hypercholesterolemia is:				
Certain when >8 point				
Probable when 6-8 poi				
Possible when 3-5 point				

1. High-density lipoprotein cholesterol and triglycerides are normal.

ApoB = apolipoprotein B; DNA = deoxyribonucleic acid; LDL-C = low-density lipoprotein cholesterol; LDL-R = low-density lipoprotein receptor; PCSK9 = proprotein convertase subtilisin/kexin type 9. Sources:

World Health Organization. Familial hypercholesterolaemia (FH): report of a second WHO consultation. 04 September 1998. http://whqlibdoc.who.int/hq/1999/WHO HGN FH CONS 99.2.pdf. Accessed 21 April 2022

## APPENDIX D: SIMON BROOME REGISTER DIAGNOSTIC CRITERIA FOR FAMILIAL HYPERCHOLESTEROLEMIA

#### **Definite Familial Hypercholesterolemia:**

Required laboratory = high cholesterol levels:

• Adult = Total cholesterol (TC) levels >290 mg/dL (>7.5 mmol/L) or low-density lipoprotein (LDL) cholesterol (LDL-C) >190 mg/dL (>4.9 mmol/L).

Note: Qualifying TC and LDL-C values for the Simon Broome Register Diagnostic Criteria for Familial Hypercholesterolemia may be fulfilled by historical values.

#### Plus at least 1 of the 2:

- Physical finding = tendon xanthomas, or tendon xanthomas in first- or second-degree relative;
   OR
- DNA-based evidence of an LDL-receptor mutation, familial defective apolipoprotein B-100, or a proprotein convertase subtilisin/kexin type 9 mutation.

#### Possible Familial Hypercholesterolemia:

Laboratory = high cholesterol levels:

• Adult = TC levels  $\geq$ 290 mg/dL ( $\geq$ 7.5 mmol/L) or LDL-C  $\geq$ 190 mg/dL ( $\geq$ 4.9 mmol/L).

Note: Qualifying TC and LDL-C values for the Simon Broome Register Diagnostic Criteria for Familial Hypercholesterolemia may be fulfilled by historical values.

#### Plus at least 1 of the 2:

- Family history of at least 1 of the following:
  - o Family history of myocardial infarction at:
    - Age 60 years or younger in first-degree relative; or
    - Age 50 years or younger in second-degree relative.

#### OR

- Family history of elevated TC:
  - o >290 mg/dL (>7.5 mmol/L) in adult first- or second-degree relative; or
  - o >260 mg/dL (>6.7 mmol/L) in child, brother, or sister aged younger than 16 years.

Source: Raal FJ, Kallend D, Ray KK, et al. Inclisiran for the treatment of heterozygous familial hypercholesterolemia. *N Engl J Med.* 2020;382(16):1520-1530

## APPENDIX E: CORRECTION FACTORS FOR LIPID-MODIFYING DRUGS

Lipid-Modifying Drug		
Dose	Reduction in Percentage	Correction Factor 
Atorvastatin		
10 mg	37	1.59
20 mg	43	1.75
40 mg	49	1.96
80 mg	55	2.22
Fluvastatin		
20 mg	21	1.27
40 mg	27	1.37
80 mg	33	1.49
Pravastatin		
10 mg	20	1.25
20 mg	24	1.32
40 mg	39	1.64
Rosuvastatin		
5 mg	38	1.61
10 mg	43	1.75
20 mg	48	1.92
40 mg	53	2.13
Simvastatin		
5 mg	23	1.30
10 mg	27	1.37
20 mg	32	1.47
40 mg	37	1.59
Statin/Ezetimibe		
Low-dose/10 mg	44	1.79
Mid-dose/10 mg	45	1.81
High-dose/10 mg	53	2.13
Ezetimibe		
10 mg	19	1.23

Correction factor = 100/(100 - reduction in percentage).

Sources

2004;58(8):746-755

Davidson MH, Ballantyne CM, Kerzner B, et al. Efficacy and safety of ezetimibe coadministered with statins: randomised, placebo-controlled, blinded experience in 2382 patients with primary hypercholesterolemia. *Int J Clin Pract*.

Source: Besseling J, Kindt I, Hof M, et al. Severe heterozygous familial hypercholesterolemia and risk for cardiovascular disease: a study of a cohort of 14,000 mutation carriers. *Atherosclerosis*. 2014;233(1):219-223

1. The correction factor should be multiplied by a historical or Screening LDL-C value. For example, a patient taking atorvastatin 80 mg, with an LDL-C of 93 mg/dL, has the equivalent of an "off-treatment" LDL-C value of 206.46 mg/dL (93 mg/dL × 2.22 = 206.46 mg/dL).

LDL-C = low-density lipoprotein cholesterol.

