#### Diagnosis of HeFH:

Diagnosis must be made by either prior historical genotyping or by clinical assessment using either the WHO Criteria/Dutch Lipid Clinic Network Criteria with a score that is ≥3 points, as specified in Appendix C, or the Simon Broome Register Diagnostic Criteria with an assessment of "Possible HeFH" or "Definite HeFH," as specified in Appendix D. 17,18 LDL-C values are required to assess the Dutch Lipid Clinic Network Criteria and/or Simon Broome Register Diagnostic Criteria. In some cases, historical lipid values may not be obtainable, as participants may have initiated lipid-modifying therapies years prior. In these instances, the Investigator will need to estimate an "off-treatment" LDL-C value to calculate whether the participant qualifies for the study. For this purpose, Appendix E contains correction factors for a variety

of statins and/or ezetimibe. The current LDL-C value obtained most recently and/or through the screening process can be converted using the appropriate correction factor. This value will be used to assess whether the participant meets either the Dutch Lipid Clinic Network Criteria or the Simon Broome Register Diagnostic Criteria. Participants with a diagnosis of HeFH may or may not have a history of ASCVD or ASCVD-risk equivalents;

History of ASCVD, defined by at least 1 of the following conditions:

- o Coronary artery disease:
  - MI;
  - Prior coronary revascularization (percutaneous coronary intervention [PCI] or coronary artery bypass grafting [CABG]);
  - Angiographic or computed tomography (CT) imaging (eg, multidetector CT or CT angiography) evidence of coronary atherosclerosis with >70% stenosis in at least 1 major epicardial coronary artery; or
  - Coronary calcium score >100 Agatston units within 6 months prior to Screening (Visit 1).
- o Cerebrovascular disease:
  - Prior ischemic stroke confirmed by a brain imaging study (CT or magnetic resonance imaging), considered not to be caused by atrial fibrillation, valvular heart disease, or mural thrombus;
  - Carotid artery stenosis >70% on prior angiography or ultrasound; or
  - History of percutaneous or surgical carotid artery revascularization.
- o Peripheral arterial disease:
  - Prior documentation of a resting ankle-brachial index  $\leq 0.85$ ;
  - History of percutaneous or surgical revascularization of an iliac, femoral, or popliteal artery; or
  - Prior non-traumatic amputation of a lower extremity due to peripheral artery disease.

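### Protocol Appendix E gives high-dose statin plus ezetimibe a smaller correction factor (2.13) than atorvastatin 80 mg alone (2.22), so a table used to assess HeFH contradicts itself

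*Protocol*

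**What the plan says.** Protocol section 4.1 (inclusion criterion 3) allows HeFH to be diagnosed by earlier genotyping or clinically, by the Dutch Lipid Clinic Network or Simon Broome criteria. Both clinical routes use LDL-C. When historical lipids are out of reach, "the Investigator will need to estimate an 'off-treatment' LDL-C value to calculate whether the participant qualifies for the study", using Appendix E.

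Appendix E states its rule as "Correction factor = 100/(100 - reduction in percentage") and says how to apply it: "The correction factor should be multiplied by a historical or Screening LDL-C value". The entries that matter here are:

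- atorvastatin 40 mg: 49%, factor 1.96; 80 mg: 55%, factor 2.22
- rosuvastatin 20 mg: 48%, factor 1.92; 40 mg: 53%, factor 2.13
- ezetimibe 10 mg alone: 19%, factor 1.23
- statin with ezetimibe: "Low-dose/10 mg 44 1.79", "Mid-dose/10 mg 45 1.81" and "High-dose/10 mg 53 2.13"

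The appendix does not say which statins and doses are low, mid or high. Its worked example is a patient on atorvastatin 80 mg: "93 mg/dL × 2.22 = 206.46 mg/dL".

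**The concern.** A correction factor should undo the effect of treatment. If a second LDL-lowering drug is added and the measured value is the same, the implied untreated value should not go down. For atorvastatin 80 mg it does, and for rosuvastatin 40 mg it does not move, in a table that elsewhere gives ezetimibe an effect of its own.

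The derived value feeds HeFH status. For a person without ASCVD, that status decides eligibility and whether they count towards the 20% cap. For others it sets the randomisation stratum. It is also a covariate in the primary ANCOVA and the imputation model (SAP 3.4.1), a stratification factor in the time-to-event analyses (SAP 3.4.3), and part of a subgroup defined by diagnostic certainty (SAP 3.4.4). At least 70% of participants must take a high-intensity statin and ezetimibe is permitted, so the regimens concerned are ordinary ones in this trial.

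**Working it through.** **1. Reproduce the table.** Applying 100/(100 − reduction) to all 22 rows and rounding to two decimals returns 21 of the printed factors. Examples: 100/45 = 2.22, 100/47 = 2.13, 100/81 = 1.23. The exception is the mid-dose combination row: 100/55 = 1.818, which rounds to 1.82, against 1.81 printed. The worked example also reproduces: 93 × 2.22 = 206.46 mg/dL.

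**2. Same measured value, ezetimibe added.** 93 × 2.13 = 198.09 mg/dL. The derived untreated value falls by 1 − 198.09/206.46 = 4.1%. Both values stay in the Dutch 190–249 mg/dL band and above the Simon Broome 190 mg/dL limit, so this patient's class does not change.

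**3. Where class can change, with no added assumption.** The measured LDL-C needed to reach 190 mg/dL is 190/2.22 = 85.6 on atorvastatin 80 mg alone and 190/2.13 = 89.2 with ezetimibe. Combination users between about 85.6 and 89.2 mg/dL miss a limit that the same measurement would meet on the statin alone. This window lies inside the 55 to <100 mg/dL entry tier of inclusion criterion 5.

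**4. Which regimens invert.** Taking 2.13 as a ratio to the single-statin factor:

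- atorvastatin 80 mg: 2.13/2.22 = 0.96 (inverts)
- rosuvastatin 40 mg: 2.13/2.13 = 1.00 (ties)
- atorvastatin 40 mg: 2.13/1.96 = 1.09 (rises)
- rosuvastatin 20 mg: 2.13/1.92 = 1.11 (rises)

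If a site read atorvastatin 40 mg or rosuvastatin 20 mg as mid-dose (1.81), these two would invert as well: 1.81/1.96 = 0.92 and 1.81/1.92 = 0.94.

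**5. Size under an added assumption.** Suppose that ezetimibe's 19% acts proportionally on top of any statin, and that all four regimens count as high-dose. The documents state neither. The benchmark factor is then the statin factor × 1.23, and the shortfall is 1 − 2.13/benchmark.

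| Regimen with ezetimibe | Benchmark | Shortfall | Measured LDL-C scored below 190 only because 2.13 is used (mg/dL) |
|---|---|---|---|
| Atorvastatin 80 mg | 2.73 | 22% | 69.6–89.2 |
| Rosuvastatin 40 mg | 2.62 | 19% | 72.5–89.2 |
| Atorvastatin 40 mg | 2.41 | 12% | 78.8–89.2 |
| Rosuvastatin 20 mg | 2.36 | 10% | 80.5–89.2 |

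Under the same assumption, the worked patient's LDL-C would fall to 93 × 0.81 = 75.33 mg/dL once ezetimibe was added, and would convert to 75.33 × 2.13 = 160.45 mg/dL. That is below 190, where the same person had derived 206.46 before. For this patient any further fall above 1 − 190/198.09 = 4.1% is enough to drop below 190.

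**6. The other direction.** Against the same benchmark, the low-dose combination row (1.79) over-corrects for some low-potency statins: pravastatin 10 mg (1.25 × 1.23 = 1.54, +16%), fluvastatin 20 mg (1.27 × 1.23 = 1.56, +15%) and simvastatin 5 mg (1.30 × 1.23 = 1.60, +12%).

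**The case against.** A reader might infer that combination users in general are under-scored for HeFH. The documents do not support that. The strict inversion is confined to atorvastatin 80 mg, with a tie at rosuvastatin 40 mg. Elsewhere the answer depends on undefined dose bands, and for some weak statins the error runs the other way. The 10% to 22% figures need ezetimibe's stand-alone 19% to multiply fully onto each statin, and Appendix E does not present it as an add-on effect. The appendix cites several sources, and its single-statin and combination rows may come from different ones. All of this stands. It limits the size of the point but does not make the rows agree.

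The exposed group is also narrow. Genotyping and historical lipids bypass the factors. Simon Broome has a total-cholesterol route and requires further evidence besides a lipid value. Participants with ASCVD remain eligible whatever their HeFH status. The documents do not say how many people are affected, and the 70% high-intensity share is not an estimate of that number.

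A reader might also infer bias in the treatment effect. That does not follow. The estimate is made before randomisation, so any misclassification arises in the same way in both arms. The primary model uses the IRT strata as recorded at randomisation (SAP 3.4.1), and the sensitivity analysis on eCRF strata runs only if more than 10% of participants disagree.

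The mid-dose discrepancy is minor: 190/1.81 = 105.0 against 190/1.82 = 104.4 mg/dL. An unrounded reduction of 44.8% would give 1.81, so it need not be a calculation error.

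**Conclusion.** The point holds as an internal inconsistency in an eligibility and stratification rule. Nothing else in the Protocol or SAP repairs it. What rests on the table alone is the inversion for atorvastatin 80 mg (2.13 against 2.22), the tie for rosuvastatin 40 mg, and a window of about 85.6 to 89.2 mg/dL in which the 190 mg/dL limit is missed. The 10% to 22% under-correction is conditional on proportional action and on all four regimens being high-dose.

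The consequence is limited to participants who have neither genotyping nor historical lipids and whose derived value crosses a limit. For those without ASCVD it touches eligibility and the 20% cap. For others it touches the HeFH stratum and covariate. It does not bias the primary comparison, and the sample-size calculation does not depend on it. The documents do not show which factor is right, and this review does not choose one.

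**What to change.** In Protocol Appendix E:

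- Reconcile the three statin/ezetimibe rows with the single-statin rows.
- Define low, mid and high dose by named statin and dose. SAP 3.1.10 uses a separate high-intensity definition for Japan, so the appendix should say whether its bands differ there too.
- State that a combination factor may not be below the factor for that statin dose alone.
- Reconcile the mid-dose row with the stated formula (45% gives 1.82; 1.81 is printed).

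Multiplying the statin factor by 1.23 is one conceivable replacement. It imports the proportional assumption and would lower the factor for some low-potency statins, so it should not be adopted without support.

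Where the eCRF holds the inputs, check before unblinding the HeFH class of combination users whose untreated LDL-C was estimated. The documents do not confirm that those inputs were collected, since SAP 3.1.10 refers only to CV history in the eCRF.

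The cost is appendix wording and, if feasible, one data check. The downside is that a few participants may change eCRF class relative to IRT, which would count towards the 10% trigger for the fourth sensitivity analysis. The primary model keeps the IRT strata. The check cannot recover anyone already screened out.

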# APPENDIX F: ENDPOINT DEFINITIONS PER THE 2017 CARDIOVASCULAR AND STROKE ENDPOINT DEFINITIONS FOR CLINICAL TRIALS

#### CARDIOVASCULAR DEATH

Cardiovascular (CV) death includes death resulting from an acute myocardial infarction (MI), sudden cardiac death, death due to heart failure (HF), death due to stroke, death due to CV procedures, death due to CV hemorrhage, and death due to other CV causes.

Classifying CV mortality more specifically (MI, sudden death, etc) is usually not needed for outcome trials. Moreover, such classification is difficult because the classifications refer both to underlying cause (eg, acute MI, which can cause fatal arrhythmias or HF) and to mode of death (sudden/arrhythmic; HF, which can result from an MI or worsening HF), and they overlap substantially. The following definitions can, however, be used if desired:

1. Death due to acute MI refers to death by any CV mechanism (eg, arrhythmia, sudden death, HF, stroke, pulmonary embolus, peripheral arterial disease) ≤30 days² after an MI, related to the immediate consequences of the MI, such as progressive HF or recalcitrant arrhythmia. We note that there may be assessable mechanisms of CV death during this time period, but for simplicity, if the CV death occurs ≤30 days after the MI, it will be considered a death due to MI.

Acute MI should be verified to the extent possible by the diagnostic criteria outlined for acute MI or by autopsy findings showing recent MI or recent coronary thrombosis.

Death resulting from a procedure to treat an MI (percutaneous coronary intervention [PCI], coronary artery bypass graft [CABG] surgery), or to treat a complication resulting from MI, should also be considered a death due to acute MI.

Death resulting from an elective coronary procedure to treat myocardial ischemia (ie, chronic stable angina) or death due to an MI that occurs as a direct consequence of a CV investigation/procedure/operation should be considered a death due to a CV procedure.

- 2. Sudden cardiac death refers to death that occurs unexpectedly and not within 30 days of an acute MI. Sudden cardiac death includes the following scenarios:
  - a. Death witnessed and occurring without new or worsening symptoms;
  - b. Death witnessed within 60 minutes of the onset of new or worsening cardiac symptoms, unless the symptoms suggest acute MI;
  - c. Death witnessed and attributed to an identified arrhythmia (eg, captured on an electrocardiogram [ECG], witnessed on a monitor, or unwitnessed but found on implantable cardioverter-defibrillator [ICD] review);

<sup>2 The 30 day cut-off is arbitrary.

- d. Death after unsuccessful resuscitation from cardiac arrest (eg, ICD unresponsive sudden cardiac death, pulseless electrical activity arrest);
- e. Death after successful resuscitation from cardiac arrest and without identification of a specific cardiac or non-cardiac etiology; and
- f. Unwitnessed death in a participant seen alive and clinically stable ≤24 hours prior to being found dead without any evidence supporting a specific non-CV cause of death (information regarding the participant's clinical status preceding death should be provided, if available).

#### **General considerations:**

Unless additional information suggests an alternate specific cause of death (eg, death due to other CV causes), if a participant is seen alive within ≤24 hours of being found dead, sudden cardiac death (Criterion 2f) should be recorded. For participants who were not observed alive within 24 hours of death, undetermined cause of death should be recorded (eg, a participant found dead in bed, but who had not been seen by family for >24 hours).

- 3. Death due to HF refers to death in association with clinically worsening symptoms and/or signs of HF regardless of HF etiology. Deaths due to HF can have various etiologies, including single or recurrent MIs, ischemic or non-ischemic cardiomyopathy, hypertension, or valvular disease.
- 4. Death due to stroke refers to death after a stroke that is either a direct consequence of the stroke or a complication of the stroke. Acute stroke should be verified to the extent possible by the diagnostic criteria outlined for stroke.
- 5. Death due to CV procedures refers to death caused by the immediate complications of a cardiac procedure.
- 6. Death due to CV hemorrhage refers to death related to hemorrhage such as a non-stroke intracranial hemorrhage (eg, subdural hematoma), non-procedural or non-traumatic vascular rupture (eg, aortic aneurysm), or hemorrhage causing cardiac tamponade.
- 7. Death due to other CV causes refers to CV death not included in the above categories but with a specific, known cause (eg, pulmonary embolism or peripheral arterial disease).

#### NON-CARDIOVASCULAR DEATH

Non-CV death is defined as any death with a specific cause that is not thought to be CV in nature. Detailed recommendations on the classification of non-CV causes of death are beyond the scope of this appendix. The level of detail required and the optimum classification will depend on the nature of the study population and the anticipated number and type of non-CV deaths. Any specific anticipated safety concern should be included as a separate cause of death. The following is a suggested list of non-CV causes of death:

- Pulmonary;
- Renal;
- Gastrointestinal;
- Hepatobiliary;
- Pancreatic;
- Infection (includes sepsis);
- Inflammatory (eg, Systemic Inflammatory Response Syndrome, other immune conditions [including autoimmune]; may include anaphylaxis from environmental factors [eg, food allergies]);
- Hemorrhage that is neither CV bleeding nor a stroke;
- Non-CV procedure or surgery;
- Trauma (includes homicide);
- Suicide;
- Non-prescription drug reaction or overdose;
- Prescription drug reaction or overdose (may include anaphylaxis);
- Neurological (non-CV) (excludes CV death from ischemic stroke, hemorrhagic stroke, or undetermined cause of stroke or CV hemorrhage of central nervous system);
- Malignancy (eg, leukemia, lymphoma, or other malignancy); and
- Other non-CV.

#### UNDETERMINED CAUSE OF DEATH

Undetermined cause of death refers to death not attributable to 1 of the above categories of CV death or to a non-CV cause. Inability to classify the cause of death may be due to lack of information (eg, the only available information is "participant died") or when there is insufficient supporting information or detail to assign the cause of death. In general, most deaths should be classifiable as CV or non-CV, and the use of this category of death, therefore, should be discouraged and should apply to few participants in well-run clinical studies.

A common analytic approach for cause of death analyses is to assume that all undetermined cases are included in the CV category (eg, presumed CV death, specifically "death due to other CV causes"). Nevertheless, the appropriate classification and analysis of undetermined causes of death depends on the population, the intervention under investigation, the duration of follow-up, and the disease process (presuming CV death does not seem appropriate, for example, for people with late stage cancer, advanced pulmonary disease, long-standing infections, etc). The approach should be prespecified and described in the protocol and other study documentation such as the endpoint adjudication procedures and/or the Statistical Analysis Plan.

#### **UNSTABLE ANGINA**

Unstable angina requiring hospitalization is defined as all of the following:

- 1. Ischemic discomfort (angina or symptoms thought to be equivalent) ≥10 minutes in duration occurring:
  - o At rest; or
  - o In an accelerating pattern with frequent episodes associated with progressively decreased exercise capacity.
- 2. Prompting an unscheduled hospitalization within 24 hours of the most recent symptoms. Hospitalization is defined as an admission to an inpatient unit or a visit to an emergency department that results in at least a 24-hour stay (or a change in calendar date if the hospital admission or discharge times are not available).
- 3. At least 1 of the following:
  - a. New or worsening ST or T wave changes on resting ECG (in the absence of confounders, such as left bundle branch block or left ventricular hypertrophy) as follows:
    - Transient ST elevation (duration <20 minutes), defined as a new ST elevation at the J point in 2 contiguous leads with the following cut-points: ≥0.1 mV in all leads other than leads V2 to V3 where the following cut-points apply: ≥0.2 mV in men ≥40 years (≥0.25 mV in men <40 years) or ≥0.15 mV in women; or

    - ST depression and T-wave changes, defined as new horizontal or down-sloping ST depression ≥0.05 mV in 2 contiguous leads and/or new T-wave inversion ≥0.3 mV in 2 contiguous leads with prominent R wave or R/S ratio >1.
  - b. Definite evidence of inducible myocardial ischemia as demonstrated by:
    - An early positive exercise stress test, defined as an ST elevation or ≥2 mm ST depression prior to 5 metabolic equivalents;

